8.5.2.3. Subgroup Analyses

The primary endpoint analysis will be performed for the following subgroups:

- Truth standard category: histopathology, correlative imaging, PSA response following locoregional RT
- Truth standard of each correlative imaging method
- Age: $<65, \ge 65$
- Race: White, Black or African American, Other
- Ethnicity: Not Hispanic or Latino, Hispanic or Latino

- Baseline PSA, categorized as < 0.2 ng/mL, 0.2-<0.5 ng/mL, 0.5-<1 ng/mL, 1-<2 ng/mL, 2-<5 ng/mL, ≥5 ng/mL and the same PSA categories by historical therapy modality (prostatectomy alone, prior radiation therapy, both prostatectomy and prior radiation therapy)
- Historical initial therapy modality(ies) for prostate cancer at study entry: surgery (radical prostatectomy), radiation therapy (to the prostate gland), surgery and radiation therapy, prior androgen deprivation therapy (ADT), ADT and radiation therapy
- Baseline Screening imaging modality, categorized as fluciclovine PET/CT, choline PET, NaF PET, Pelvic CT/MRI, Abdomen CT/MRI, Chest CT/MRI, bone scintigraphy
- Study center: the distribution of treated subjects by center will be created at the end of the study. Small centers with five or fewer treated subjects may be combined into one or more centers for analysis.
- Size of largest lesion (long axis) detected on the PyL image by the central imaging readers: 0-<0.5 cm, 0.5-<1.0 cm, ≥1.0 cm
- Maximum standard uptake value (SUVmax) reported for the subject's lesion(s) on the PyL image by the central imaging readers: ≤2, 2-<5, 5-<10, ≥10
- Time of PyL scan following dosing: < 60 minutes, 60-<90 minutes, 90-≤ 120 minutes, > 120 minutes
- Time since discontinuation of ADT until study entry for subjects with prior ADT use

Subgroup analyses will be performed by tabulating the primary endpoint for each subgroup. For the analysis of the endpoint by SUVmax the tabulations will use the SUVmax value adjusted for lesion long axis. This value is the predicted SUVmax from a logistic regression model of CLR (0=No,, 1=Yes) for subjects with a positive PyL scan as assessed by the central reader, including SUVmax and lesion size (long axis as reported by the central reader). This analysis will be used if the lesion size term is significant at an alpha of 0.05. If the lesion size term is not significant the unadjusted SUVmax values will be used as reported by the central reader in the tabulations.

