8.5.5. Other Efficacy Data

Summaries will be created for the following recorded measurements:

- Pathology results by lesion location and region
- Imaging results by lesion location and anatomic region for the central imaging readers, the imaging truth panel and the local site interpretation
- Lesion sizes by lesion location as recorded by the central imaging readers (and Imaging Truth Panel), excluding lesions indicated as unmeasurable
- SUV_{max}, and SUV_{mean} as recorded by the central imaging readers by lesion location
- The number of lesions detected per subject per CLR lesion location and per region (prostatic, pelvic, extra-pelvic)

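### The size-adjusted SUVmax in the CLR-by-SUVmax table is defined as the prediction of a logistic model of CLR, which cannot predict an SUVmax

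*SAP*

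**What the plan says.** SAP 8.5.2.3 lists maximum SUV among the CLR subgroups, with bands on the SUV scale: "by the central imaging readers: ≤2, 2-<5, 5-<10, ≥10". For this subgroup, "the tabulations will use the SUVmax value adjusted for lesion long axis", and the adjusted value is defined thus: "This value is the predicted SUVmax from a logistic regression model of CLR". The outcome is coded 0/1, the subjects are those with a scan read as positive by the central reader, and the covariates are SUVmax and long axis.

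A significance test decides whether the adjusted value is used: "This analysis will be used if the lesion size term is significant at an alpha of 0.05". Failing that, "If the lesion size term is not significant the unadjusted SUVmax values will be used", as the central reader reported them.

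The resulting display is Table 14.2.1.4 (SAP 11.1). No other section defines the adjusted value. SAP 8.5.5 also summarises SUVmax, but only "as recorded by the central imaging readers by lesion location", so not against CLR.

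**The concern.** A logistic regression of CLR on SUVmax and lesion size takes SUVmax as an input and returns a probability. The SAP names that output an SUVmax and sends it to bands cut at 2, 5 and 10 SUV units. As written, the instruction cannot produce what it describes.

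Someone must therefore substitute another model or other cut points. The need shows itself only when a p-value from a model of CLR falls below 0.05, that is, when CLR is already known. The model appears to be fitted separately for each central reader, so one reader's column could hold adjusted values and another's reported values. At stake is the only planned display of how CLR varies with SUVmax.

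Separately, a reported SUVmax of exactly 2 belongs to both of the two lowest bands.

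**Working it through.** **Inputs from the SAP.** Outcome, covariates, switch and bands are those of 8.5.2.3. The number of positive scans comes from SAP 7.1, where a 95% interval of half-width 0.10 around a CLR of 30% gives n = 1.96² × 0.3 × 0.7 / 0.10² = 80.67, rounded up to 81. That reproduces the plan's figure; it serves here only as a realistic n.

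**Core check, free of assumptions.** The specified model is

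logit P(CLR=1) = b0 + b1 × SUVmax + b2 × size.

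Its fitted value is a probability between 0 and 1. Since 1 < 2, every subject falls in the ≤2 band, whatever the data. The logit scale does not help: a logit above 2 needs a fitted probability above 1/(1+e⁻²) = 0.88, and a logit of 5 or more needs at least 1/(1+e⁻⁵) = 0.993. Nearly all subjects would still sit in the lowest band.

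**Possible repairs.**

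1. Keep the fitted probability and invent new cut points. This tabulates CLR against a score fitted to CLR and mixes the size effect into a table labelled SUVmax.
2. Invert the model: find the SUVmax that gives the same linear predictor at mean size. Algebra gives SUVmax + (b2/b1) × (size − mean size), which can be negative and is unstable when b1 is near zero.
3. Predict SUVmax from size by linear regression.
4. Take the residual of log SUVmax after regression on size, re-centred at the mean.

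**Illustration with assumed inputs.** The documents give no distributions for size or SUVmax. Assumed: long axis lognormal (median 0.9 cm, log SD 0.5); SUVmax lognormal (median 7, log SD 0.8); log-scale correlation 0.5; CLR 60%; odds ratio 2 per SD of long axis; odds ratio 2 or 1 per SD of log SUVmax; n = 81; 3,000 simulated trials per setting, keeping those in which the size term had p<0.05. The gap is CLR in the top tertile minus CLR in the bottom tertile, in percentage points.

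| Value tabulated | % in ≤2 / 2-<5 / 5-<10 / ≥10 (SUVmax OR 2) | Gap, SUVmax OR 2 | Gap, no SUVmax effect |
|---|---|---|---|
| Reported SUVmax | 6 / 28 / 34 / 33 | 41 | 15 |
| Fitted probability | 100 / 0 / 0 / 0 | 52 | 37 |
| Inverted model | 40 / 9 / 12 / 40 | 49 | −8 |
| SUVmax predicted from size | 0 / 6 / 58 / 36 | 47 | 35 |
| Size-adjusted log residual | 4 / 28 / 38 / 31 | 24 | −2 |

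About 33% of inverted values are negative. With no true SUVmax effect, the table could show a strong relation (37 or 35 points) or essentially none (−2), depending on the repair.

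Over 12 settings (SUVmax odds ratio 1 or 2, correlation 0 or 0.5, CLR 30, 60 or 85%) the gaps run from 26 to 52 (fitted), −11 to 49 (inverted), −2 to 47 (predicted) and −3 to 30 (residual). With no SUVmax effect and zero correlation, the fitted value has rank correlation 0.93 to 0.95 with size and −0.03 to 0.05 with SUVmax, so a table built on it would largely repeat the lesion-size table.

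**How often the switch is met.** This cannot be known from the documents. Under the same distributions it is 3–5% of trials with no size effect. At a size odds ratio of 2 it is 19–77% with n = 81, and 10–58% with n = 55. The smaller n supposes that about a third of subjects lack a measurable long axis; SAP 8.5.5 allows for such lesions, summarising sizes "excluding lesions indicated as unmeasurable". Trials with fewer than 3 subjects in either outcome class, or with a separated fit, were skipped (at most 7% at n = 81, 10% at n = 55).

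**The case against.** The defect is conditional. If the size term is not significant, reported SUVmax is used and the table is sound apart from the band overlap; with no size effect that is the usual case. This stands and limits the point.

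The SAP Introduction commits to settling decisions about the final analysis before database lock unless the regulator is told. That is a real safeguard against silent repair, and a post hoc choice is a prediction rather than something the plan states. But the commitment supplies no definition, and a problem that appears only once the CLR model is fitted is easily missed before lock.

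The illustration is favourable to the concern: in the setting with both odds ratios at 2, the fitted, inverted and predicted gaps are the upper ends of their ranges, and a CLR of 60% is twice the planning value. At 30% with the other inputs unchanged, the gaps are 47 (fitted), 44 (inverted), 42 (predicted) and 19 (residual), so the readings still differ. It is also fair that several readings are models the SAP does not mention, and that nobody would keep an inversion giving negative SUVmax values. The core point needs none of these figures.

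Lesion size has its own CLR table (14.2.1.3.1), so the size effect can be seen directly. That limits the harm but leaves the SUVmax table without a definition.

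**Conclusion.** The concern holds. The rule is wrong as written, not merely short of detail: a logistic model of CLR with SUVmax as a covariate yields a probability or a logit, never an SUVmax, and literal use puts 100% of subjects in one band. That conclusion follows from the form of the model and rests on no assumption. The differences among repairs, and the frequency with which the switch is met, rest on the assumed inputs and are illustrative only.

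The consequence is minor. It touches one descriptive subgroup table, and only when the lesion-size term has p<0.05. The primary CLR test, its confidence interval, the sample size and the secondary endpoint are unaffected. The band overlap at exactly 2 is a small separate slip that applies whether or not the adjustment is used.

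**What to change.** In SAP 8.5.2.3, tabulate CLR by reader-reported SUVmax for every central reader, in the bands <2, 2-<5, 5-<10 and ≥10. Delete the predicted value and the p<0.05 switch.

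If size adjustment is wanted, report it separately as one named analysis: either the SUVmax odds ratio adjusted for long axis, from the logistic model already described, or CLR by a size-adjusted SUVmax obtained from a linear regression of log SUVmax on long axis that leaves CLR out.

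At minimum, name the intended model and state how its output maps to the bands; that alone cures the missing definition. Removing the switch as well keeps the table on the same scale for all three readers.

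The cost is SAP wording only. No new data are needed, and the programming becomes simpler.

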8.5.2.4. Multiple Comparisons and Multiplicity

There will be no correction for multiple comparisons as there is a single primary endpoint based on a composite truth standard where each subject is evaluated with only a single truth standard source.

8.5.3. Analysis of Secondary Efficacy Endpoints

The secondary efficacy endpoint, change in planned medical management, will be generated on the FAS for all subjects regardless of finding(s) on PyL PET/CT imaging, and be analyzed by calculating a two-sided 95% CI for the proportion of subjects with any change in planned management as a binary variable. The summary will present the respective proportions and CIs calculated using a normal approximation to the binomial distribution if the statistical assumptions are met.

The analysis will present the percentage of subjects with a shift between no planned treatment and the major categories of planned therapy as well as between major categories defined in Table

Statistical Analysis Plan: Protocol PyL3301

5 by the local imaging readers' results and for all subjects combined. An additional tabulation will be presented for the changes in planned therapy between major categories of therapy by the results reported by the central PyL readers

A summary of shifts in planned management from Pre- and to Post- ¹⁸F-DCFPyL imaging evaluations will also be presented for shifts between the specific categories of treatments within local therapies (Table 6). These shifts will also be summarized by the results of the local reader of the PyL scan and by the results reported by the three central readers.

Table 6: Shifts in Planned Therapy

Pre- ¹⁸ F-DCFPyL PET/CT scan	Post- ¹⁸ F-DCFPyL PET/CT scan	
No treatment planned	Focal therapy	
Focal therapy	No treatment planned	
No treatment planned	Salvage surgery	
Salvage surgery	No treatment planned	

Another presentation of the change in planned management of the subject's disease will be a tabulation of all post-dose treatments against the pre-dose assessment.

The shifts within individual categories as well as an all shifts from pre- to post-PyL scan assessments will be presented with the number and percent of subjects with the respective change in shift tables, by the results reported by the local and central PyL readers. All pre- and post-PyL scan assessments will be presented with the assessment of change in a data listing.

8.5.4. Analysis of Exploratory Efficacy Endpoints

Exploratory efficacy endpoints will be generated using the FAS to calculate detection rates on the subset of the FAS with at least one positive lesion identified by PyL PET/CT imaging for PPV and false positive scan rate endpoints. If a subject has more than one truth standard modality, (i.e., an image-guided biopsy and a correlative imaging scan) the information from the modality(ies) not used for the primary endpoint will be utilized in the calculation of exploratory endpoints. As there are results reported for three independent readers, these summary tables will present the respective endpoints for each reader.

The following endpoints will be analyzed using a two-sided 95% CI presented for each central imaging reviewer and for the local site interpretation separately based on a normal approximation to the binomial:

- Detection rates of ¹⁸F-DCFPyL PET/CT imaging by lesions in the following regions: prostatic, pelvic, extra-pelvic lymph nodes, extra-pelvic bone and extra-pelvic other defined in Table 3 in Section 8.5.2.1
- Detection rates of ¹⁸F-DCFPyL PET/CT imaging by lesions in the following regions: prostatic, pelvic, extra-pelvic (lymph nodes, bone and other combined) defined in Table 3 in Section 8.5.2.1
- The detection rates of ¹⁸F-DCFPyL PET/CT imaging as a function of baseline PSA groups categorized as <0.2 ng/mL, 0.2-< 0.5 ng/mL, 0.5-<1 ng/mL, 1-<2 ng/mL, 2-<5 ng/mL, ≥5 ng/mL

- Detection rates of ¹⁸F-DCFPyL PET/CT imaging by baseline Screening imaging modality, categorized as fluciclovine PET/CT, choline PET, NaF PET, Pelvic CT or MRI, Abdomen CT or MRI, Chest CT or MRI, bone scintigraphy
- The percentage of subjects with positive ¹⁸F-DCFPyL PET/CT scans assessed by the central reader who have negative findings for prostate cancer (false positive subjects) based on the composite truth standard. The percentage of false positive scans is defined as (1-CLR).
- The PPV of ¹⁸F-DCFPyL PET/CT for prostatic, pelvic, extra-pelvic lymph nodes, extra-pelvic bone and extra-pelvic other regions defined in Table 3 in Section 8.5.2.1, based on the composite truth standard in subjects with positive lesion(s) on ¹⁸F-DCFPyL PET/CT imaging
- The PPV of ¹⁸F-DCFPyL PET/CT for prostatic, pelvic and extra-pelvic (lymph nodes, bone and other combined) regions defined in Table 3 in Section 8.5.2.1, based on the composite truth standard in subjects with positive lesion(s) on ¹⁸F-DCFPyL PET/CT imaging
- The overall true positive detection rate (TPR) based on all subjects with a positive ¹⁸F-DCFPyL PET/CT regardless of positive or negative findings as assessed by the central reader, as defined in section 5.1.3. This result will be reported on the primary endpoint table.

8.5.5. Other Efficacy Data

Summaries will be created for the following recorded measurements:

- Pathology results by lesion location and region
- Imaging results by lesion location and anatomic region for the central imaging readers, the imaging truth panel and the local site interpretation
- Lesion sizes by lesion location as recorded by the central imaging readers (and Imaging Truth Panel), excluding lesions indicated as unmeasurable
- SUV_{max}, and SUV_{mean} as recorded by the central imaging readers by lesion location
- The number of lesions detected per subject per CLR lesion location and per region (prostatic, pelvic, extra-pelvic)

8.5.6. Intra- and Inter-reader Reliability Assessments

A subset of each central PyL imaging readers' scans will be evaluated twice, after a washout period of at least four weeks. The test-retest reliability of each reader will be assessed by calculating percent agreement (concordance) and Cohen's pairwise kappa and its respective 95% confidence interval for the dichotomous results (positive or negative) for all subjects with two scan interpretations.

The agreement between the three independent readers will be assessed by calculating percent pairwise concordances and Fleiss's overall multi-assessor kappa and its respective 95%

confidence interval will be calculated for the dichotomous result (positive or negative) for each scan across all subjects.

The agreement between the each of three independent readers and the local site reader will be assessed by calculating percent concordance and Cohen's pairwise kappa and its respective 95% confidence interval for the dichotomous results (positive or negative) across all subjects.

8.6. Safety Analysis

8.6.1. Adverse Events

Adverse events are captured from the time of ¹⁸F-DCFPyL administration until the scheduled safety follow-up telephone call scheduled between 5 and 11 days after dosing. All adverse events are considered treatment-emergent. Adverse events will be coded using MedDRA. The severity of each adverse event will be rated using the CTCAE 5-point scale.

8.6.1.1. Summaries of Adverse Event Incidence Rates for All Subjects

The incidence and percentage of subjects reporting a treatment-emergent AEs (TEAEs) will be summarized by MedDRA SOC and Preferred Term. If a subject reports more than one adverse event with the same preferred term, the subject will be counted once with the highest severity. Subject listings will be prepared for all adverse events, all serious AEs, all AEs leading to study discontinuation and for all deaths.

An overall summary will be prepared that presents:

- the number and proportion of subjects reporting TEAEs
- the number and proportion of subjects reporting a treatment-related TEAEs
- the number and proportion of subjects reporting TEAEs CTCAE grade 3 and above
- the number and proportion of subjects reporting TEAEs leading to study discontinuation
- the number and proportion of subjects reporting serious TEAEs, both fatal and non-fatal

Summary tables will be created for:

- the incidence, presented as the number and percent of subjects, for all TEAEs by MedDRA SOC and PT, with all relationships to study drug and severity ratings combined
- the incidence, presented as the number and percent of subjects, for all TEAEs by MedDRA SOC and PT, with all relationships to study drug and severity ratings combined, reporting only TEAEs with incidence > 5%.
- the incidence of all TEAEs by MedDRA SOC and PT for events considered related to study drug
- the incidence of all TEAEs by MedDRA SOC and PT for events by severity as expressed by CTCAE grade.

8.6.1.2. Handling of Missing and Partial AE Onset and Stop Dates

In this study, the subjects are followed up for approximately one week (± 3 days) for the onset of adverse events. All efforts will be made to avoid missing start dates. If an adverse event has a stop date prior to the safety follow-up telephone call, it is expected to have a complete date. If the event is ongoing at the time of the follow-up call, then the stop date will not be recorded. If any event has a partial start date or stop date, it will be included in the analysis of adverse events and will be considered treatment-emergent. There is no planned imputation to account for incomplete dates.

8.6.1.3. Summaries of Adverse Incidence Rates for Serious Adverse Events (SAE), Adverse Event Dropouts, and Death

The incidence of all serious AEs by MedDRA SOC and PT will be summarized by the number and percent of subjects. Similarly, the incidence of all AEs leading to study discontinuation and all deaths will be presented by MedDRA (SOC) and (PT) as summary tables.

8.6.2. Study Drug Exposure and Compliance

Each subject will receive a single intravenous injection of ¹⁸F-DCFPyL. Exposure to ¹⁸F-DCFPyL will be summarized by administered activity in mCi and volume administered in mL. The table will include the number of subjects dosed and descriptive statistics for the injection volume administered in mL and activity in mCi. A listing of drug administration will include each subject's date of administration, volume administered, and activity delivered.

8.6.3. Concomitant and Other Medications

Concomitant medications are medications taken by the subject after dosing with study drug until the end of follow-up for each subject. Medications that are ongoing at the time of dosing will also be included as concomitant medications. Medications will be coded using the WHO drug dictionary. All recorded medications will be summarized by ATC level 4 category and preferred term and presented as number and percentage of subjects in the safety population. If a subject has a specific medication recorded more than once, it will only be counted once. A subject listing will present all recorded concomitant medications, dates of administration and timing relative to dosing.

8.6.3.1. Handling of Missing and Partial Concomitant and Other Medication Start and Stop Dates

All medications are to be recorded as of the day of dosing and until the end of follow-up for the subject. All new medications are expected to have complete start dates. All medications discontinued while the subject is participating in the study should also have complete end dates. Any ongoing medications at the end of the subject's participation will not have a stop date. Medications that were ongoing at the time of subject dosing will be allowed incomplete dates if a start year is recorded. These medications will be treated as baseline medications. To calculate time since discontinuation of ADT to study entry, the 15th of the month will be substituted for missing day of the month, July will be substituted for missing month, and July 1 will be substituted for missing day and month. If the entire stop date for prior ADT use is missing, the date will be considered missing.

Statistical Analysis Plan: Protocol PyL3301 October 24, 2019

8.6.4. Laboratory Data

Only serum PSA will be assessed in this study. No other laboratory parameters are required. PSA will be an analyzed by a central laboratory. The baseline value is required for all subjects in the safety population and will be presented as descriptive statistics. For those subjects undergoing efficacy follow-up who will undergo radiation therapy, PSA will be evaluated every three months until the baseline value decreases by at least 50%, or until the subject is followed for nine months. For those subjects, the PSA values and changes from baseline will be summarized at each post-treatment visit. The number and percent of subjects who achieve the 50% reduction from baseline at each 3-month follow-up visit will be presented as an efficacy endpoint.

